## 4.2 Scientific Rationale for Study Design

School employees will participate in the intervention for up to 1 year. The pre-intervention CARE assessment battery for teachers and staff will be distributed for completion up to one month prior to the CARE teacher and staff resiliency workshop. The post-intervention CARE assessment battery will be distributed for completion at one-week post intervention and two months post-intervention.

Based on clinical experience of the investigators and published data, the one-week post intervention time point provides insight into the immediate uptake of skills and improvement in emotional well-being of participants who have completed a resiliency workshop. The two-month post-intervention time frame aids in the determination of which skills and concepts endured over time.

The resiliency workshop is delivered across one to four days during a one to four-month period to provide teachers and staff the opportunity to practice skills they have learned prior to being introduced to new concepts and techniques. The CARE team follows up with participants via email on a weekly basis to provide reminders of prior practices and context for their use. This approach has been shown to be effective for promoting teacher and staff mental health and well-being in prior iterations of this workshop. Staff will be identified as either non-administrative staff or administrative staff. Non-administrative staff and teachers attend CARE workshops together and do not include administrative staff to promote openness and feedback.

Administrative staff attend CARE workshops that are designed to meet the unique needs of principals and administrators. Specifically, at least six studies have investigated effectiveness of CARE on improving classroom learning, general participant well-being, self-efficacy, reduced burnout, improved self-awareness, self-care and compassion, and mindfulness. Additional work has demonstrated the impact of CARE on teachers' cardiovascular health, including lower heart rate.

## 4.3 Study Definition of Enrollment

Study enrollment is defined as the participant has provided informed consent and completed the pre-intervention CARE assessment battery measures (see Section 6.1).

## 4.4 Study Definition of Completion

Study participation is defined as complete after teachers and staff complete the 2-month post-intervention CARE assessment battery.

# 5 STUDY POPULATION

## 5.1 Selection of the Study Population

Adults will be screened for participation according to the criteria in Section 5.2.

## 5.2 Inclusion/Exclusion Criteria

Inclusion Criteria	

- Adult participant, defined as an adult (18 years or older) employed by a school working with youth in kindergarten through 12th grade.

- Fluent in the English language

--------------------	--

Exclusion Criteria	N/A
---------------------------	-----

## 5.3 Participant Discontinuation/Withdrawal

### 5.3.1 Participant/Parent Decides to Withdraw Consent

Participants may voluntarily withdraw consent to participate in the study at any time. Participants are not obligated to state the reason for withdrawal. No additional study data will be collected after consent has been withdrawn, however, all data collected prior to consent withdrawal will be maintained in the database.

### 5.3.2 Handling of Withdrawals

The reasons for withdrawal, or failure to provide a reason, must be documented.

Reasons of withdrawal may include the following:

1. Participants who withdraw consent to participate in the study.
2. Study Investigator/Sponsor decision

## 6 STUDY PROCEDURES

### 6.1 Summary of Procedures

Procedure	Enrollment/ Baseline	Intervention	Follow-up
Teacher and staff informed consent	X		
CARE assessments for teachers and staff	X 		X 
CARE teacher and staff resiliency workshop		X	

 Pre-intervention CARE assessment to be distributed for completion up to one month prior to the CARE teacher and staff resiliency workshop (intervention).

 Post-intervention CARE assessment to be distributed for completion one week post-intervention and two months post-intervention.

### 6.2 Enrollment/Baseline

The following data will be obtained at the time of enrollment.

- Adult teacher and staff informed consent
- CARE assessments for teachers and staff, pre-intervention (including collection of demographic variables)
  - To be distributed for completion up to one month prior to the intervention.

## 6.3 Intervention

The intervention will be a professional development workshop for teachers and staff delivered across one to four days. The CARE intervention aims to help teachers and staff handle the stresses of school-related work by offering tools and resources for reducing stress, preventing burnout, enlivening teaching, and helping students thrive socially, emotionally, and academically. Tools include mindful awareness practices and caring and emotion skills training. Each intervention workshop includes 30 to 35 participants and a facilitator, who is part of the CARE team. The workshops will be held at a location selected by the school, likely on their campus.

## 6.4 Follow-up

### 6.4.1 CARE Assessments for Teachers and Staff

The following data will be distributed for completion one week post-intervention and two months post-intervention.

- CARE assessments for teachers and staff, post-intervention (see Section 6.5.3)

## 6.5 Evaluation Details

### 6.5.1 Summary of Evaluations

Applicable informed consent will be documented for all participants. Participants will be asked to complete the pre-intervention CARE assessments online at the time of consent (up to one month before the intervention). The post-intervention CARE assessments will be completed online by participants one week after and two months after the intervention. REDCap will be used to distribute electronic consents and the pre- and post-assessments using a public link sent to the school administrator(s), who will then distribute it to the participating teachers and staff. Participants' email addresses will be collected within the REDCap survey and will be used solely for payment/incentive purposes. No additional assessments will be collected from the participants as part of this study.

Participants will be instructed that all questions are optional. The questionnaire will include the following:

- Demographic variables
- CARE Assessments

### 6.5.2 Demographic Variables

Participants will be asked a series of questions about their demographics, including their race, ethnicity, gender, school name, school role (administrative staff, non-administrative staff or teacher), and the total number of years they have taught, at current grade level and at current school. We will not share data categorized by role with school districts. We will only share aggregate data grouped by schools with school districts if there are more than 10 participants. If there are fewer than 10 participants at a school, we will group schools together to provide a summary report. If the number of workshop participants for the administrative or non-administrative staff group is less than 10, then these participants will be grouped together and identified as "staff."

### **6.5.3 CARE Assessments**

The CARE assessments are a battery of reliable and validated surveys that aim to collect teachers' and staff's self-reported self-efficacy, burnout, anxiety, depression, and stress.

The following assessments will be completed before and after the behavioral intervention:

- CARE Assessment Battery:
  - a. Teachers' Sense of Efficacy Scale;
  - b. Maslach Burnout Inventory;
  - c. Symptoms of anxiety Generalized Anxiety Disorder 7 (GAD7);
  - d. Symptoms of depression – Patient Health Questionnaire 8 (PHQ-8);
  - e. Perceived Stress Scale (PSS)
  - f. Experiences with the CARE for Professional Development Program (post-test only)

## **6.6 Participant Compensation**

Participants will receive a \$25.00 electronic Amazon gift card after completing each of the CARE assessments at baseline, one-week post-intervention, and two months post-intervention during afterschool hours. The CARE assessment battery is anticipated to take approximately 45 minutes to complete. The maximum compensation amount per participant is \$75, and a maximum of three payments will be distributed to participants. The payment amount is based on the 2022-2023 annual salaries for North Carolina teachers. Participants' names and email addresses will be shared with Amazon, Inc. so they can send participants the \$25 electronic gift card to their email address. A third-party vendor, Amazon, Inc., will be used to distribute payments.

## **7 ASSESSMENT OF SAFETY**

No safety will be recorded as part of this study.

## **8 STUDY TERMINATION**

This study may be terminated at any time by NICHD or the study principal investigators. Reasons for termination may include but are not limited to, if in their judgment, no further benefits are to be achieved from the study. If the study is terminated, notifications will be made to the IRB of record and study participants, in accordance with all applicable regulations governing the study and site/investigator.

## 9 STATISTICAL CONSIDERATIONS

### 9.1 Study Endpoints

#### 9.1.1 Primary Endpoints

Primary Objective: Examine the impact of a teacher resilience program on mental health and well-being outcomes of K-12 teachers and staff (administrative and non-administrative).

Primary Endpoint: Change in CARE assessment scores after the intervention compared to before.

- Teacher cohort 1: Change in raw CARE assessment scores (Teachers' Sense of Efficacy Scale; Maslach Burnout Inventory; Symptoms of anxiety Generalized Anxiety Disorder 7 (GAD7); Symptoms of depression - Patient Health Questionnaire 8 (PHQ-8); Perceived Stress Scale (PSS))
- Staff-non administrative cohort 2: Change in raw CARE assessment scores (Teachers' Sense of Efficacy Scale; Maslach Burnout Inventory; Symptoms of anxiety Generalized Anxiety Disorder 7 (GAD7); Symptoms of depression - Patient Health Questionnaire 8 (PHQ-8); Perceived Stress Scale (PSS))
- Staff administrative cohort 3: Change in raw CARE assessment scores (Teachers' Sense of Efficacy Scale; Maslach Burnout Inventory; Symptoms of anxiety Generalized Anxiety Disorder 7 (GAD7); Symptoms of depression - Patient Health Questionnaire 8 (PHQ-8); Perceived Stress Scale (PSS))

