#### 9.1.2 Exploratory Endpoints

Exploratory Objective: Examine teacher and staff (administrative and non-administrative) classroom instruction and behavior management.

Exploratory Endpoint: Teacher and staff (administrative and non-administrative) perceptions of changes in classroom instruction and behavior management after professional development (post-test only).

- Teacher cohort 1: Change in raw perceived changes in classroom instruction and behavior management after professional development
- Staff non-administrative cohort 2: Change in raw perceived changes in classroom instruction and behavior management after professional development
- Staff administrative cohort 3: Change in raw perceived changes in classroom instruction and behavior management after professional development

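### Change on the Teachers' Sense of Efficacy Scale is a primary endpoint in both staff cohorts, but the plan does not establish which staff have class duties, so the staff efficacy result mixes people in an unknown proportion.

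*Combined protocol and SAP*

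**What the plan says.** Section 9.1.1 defines the primary endpoint separately for teachers, non-administrative staff and administrative staff. The instrument list is the same each time and starts with the teacher efficacy scale: "Staff-non administrative cohort 2: Change in raw CARE assessment scores (Teachers' Sense of Efficacy Scale" for cohort 2 and "Staff administrative cohort 3: Change in raw CARE assessment scores (Teachers' Sense of Efficacy Scale" for cohort 3. Section 9.1.2 does likewise for the exploratory endpoint, for example "Staff administrative cohort 3: Change in raw perceived changes in classroom instruction and behavior management after professional development".

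Section 5.2 asks that a participant be an adult "employed by a school working with youth in kindergarten through 12"th grade and fluent in English. It sets no teaching requirement and no exclusions. Section 4.2 identifies who the administrators are: "Administrative staff attend CARE workshops that are designed to meet the unique needs of principals and administrators". Section 6.5.2 collects "school role (administrative staff, non-administrative staff or teacher), and the total number of years they have taught", with further years-taught questions for the current grade level and school.

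Section 6.5.3 calls the battery reliable and validated and says that it is meant to capture self-efficacy in staff as well as teachers. Section 6.5.1 makes every question optional. Section 9.3.1 plans a bootstrap 95% confidence interval for the raw change on each assessment, with no exception by role.

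**The concern.** A score for efficacy in teaching describes the respondent only if the respondent teaches or manages a class. A principal or other employee without a class can skip the scale, answer hypothetically, or give the same answer each time. The plan does not distinguish these cases. Its staff result would be an average over people with and without class duties, reported as a primary result for the whole cohort. A small change could mean that the program did little for staff who teach, or that few of the respondents teach. A large change could come from the subset who chose to answer.

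There is also a possible knock-on effect. Section 4.3 ties enrollment to completing the baseline battery, and section 9.2.1 ties the per-protocol set to completed pre and post assessments. Neither says whether leaving out one scale counts as incomplete. On a strict reading, an administrator who skips an inapplicable scale could also be lost for burnout, anxiety, depression and stress.

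**Working it through.** The plan states no sample size, power or effect size, so there is no figure of its own to reproduce. The check is a comparison of sections and a count.

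**Does the scale go to people who may not teach?**
- Sections 9.1.1 and 9.1.2: both staff cohorts receive the efficacy and the classroom endpoints.
- Section 5.2: employment at a school working with youth is enough.
- Section 6.5.2: teacher is a separate role from the two staff roles, and none of the three is defined by class duties.
- Section 4.2: administrative staff are principals and administrators, with workshops of their own.

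So the plan admits staff without class duties and assigns them the scale.

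**Does the misfit rest only on the scale's name?** No. Section 2.2 describes the self-efficacy to be promoted in school personnel as efficacy in teaching and in handling disruptive behavior. The same section expects stress reduction for teachers and staff, but names teachers alone when it comes to classroom management. The endpoints do not keep that distinction.

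**Does anything in the plan deal with it?** There is no staff version, no not-applicable option, no scoring rule for skipped items and no restriction by duty. The years-taught questions come closest, but they record teaching experience rather than present duties, and no analysis uses them.

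**How much is affected?** Counting one change per listed instrument:
- Primary, per post-intervention time point: 5 instruments × 3 cohorts = 15 changes. Efficacy in cohorts 2 and 3 makes 2 of 15 (13%).
- Over both post-intervention assessments: 2 × 2 = 4 of 15 × 2 = 30.
- If the staff groups are merged because one has fewer than 10 workshop participants (section 9.3): 5 × 2 = 10 changes, of which 1 (10%) is affected.
- Exploratory, if the concern applies there: 2 of 3 cohort results, or 1 of 2 after merging.

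**What does the staff mean estimate?** Let p be the share with class duties among staff who have an efficacy score. Then

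cohort mean change = p × (mean change with duties) + (1 − p) × (mean change without duties).

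The documents give none of these three quantities. As planned, p could lie anywhere from 0 to 1, may differ between cohorts 2 and 3, and could not be determined from the data collected.

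**The case against.** The strongest reply is that including staff is deliberate. Section 2.2 describes a whole-school approach, and section 6.5.3 says that the battery is aimed at staff too. Non-administrative staff may well include people with class duties. Results are reported by cohort, so the teacher estimate is not contaminated. There is no hypothesis test or success criterion for a staff result to trigger, and section 9.3 defers detailed methods to a statistical analysis plan due before data lock.

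Much of this stands, and it limits the point. A reader might infer that the staff efficacy results are meaningless. The documents do not support that: they do not say how many staff lack class duties, and they do not show the scale's items. A reader might also want to express the problem as a percentage dilution of the effect. No such figure follows, because the share is unknown and people who skip the scale contribute no score rather than a zero change.

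The objection is strongest for the exploratory endpoint. Section 3 names that instrument as one for teachers and staff, its items are not shown, and a principal could perceive changes in instruction without having a class.

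The reply does not remove the core of the point. A general statement that the battery is validated does not show that this scale suits people who do not teach. A later analysis plan also cannot recover present class duties if no one was asked about them.

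**Conclusion.** The point holds in a narrow form. The plan makes change in teaching efficacy a primary result in two cohorts whose members need not teach, without finding out who does. The staff efficacy change therefore has an unclear target population, most plainly among administrators. The size is 2 of 15 primary changes per time point, or 1 of 10 if the staff groups are merged.

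This rests on two assumptions: that some enrolled staff have no class duties, which eligibility allows but the documents do not quantify, and that the scale is used unadapted, since no staff form is described. For the exploratory classroom endpoint the concern is possible but unproven. A reader might extend it to every staff outcome, but nothing in the argument reaches burnout, GAD-7, PHQ-8 or PSS. It is a cheap improvement worth making and does not threaten the study as a whole.

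**What to change.** 1. Section 6.5.2: add one baseline question beside school role, such as *Do you currently instruct students or manage a class? (yes/no)*.
2. REDCap: show the efficacy scale only to those who answer yes. Do the same for any exploratory items that ask about the respondent's own class. If the follow-up surveys, sent by public link, cannot read the baseline answer, repeat the question there and define the analysis set by the baseline answer.
3. Section 9.1.1: define the efficacy endpoint by duty rather than role label. Staff with class duties are still reported within their cohort, and staff without them are not. Restricting by role label alone would discard valid scores.
4. Sections 4.3 and 9.2.1: state that a scale not shown does not make the battery incomplete.
5. Keep burnout, GAD-7, PHQ-8 and PSS in all cohorts.

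If collection has begun without the question, the statistical analysis plan should make the teacher cohort the primary efficacy result and label the staff efficacy changes as descriptive. If the sponsor has a staff version of the scale or evidence for its use in staff, citing it in section 6.5.3 would also answer the point.

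The cost is one item, branching logic and a few sentences, with fewer staff having an efficacy score. In return, the battery, expected to take about 45 minutes (section 6.6), becomes shorter for staff without a class.

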#### 9.1.2 Exploratory Endpoints

Exploratory Objective: Examine teacher and staff (administrative and non-administrative) classroom instruction and behavior management.

Exploratory Endpoint: Teacher and staff (administrative and non-administrative) perceptions of changes in classroom instruction and behavior management after professional development (post-test only).

- Teacher cohort 1: Change in raw perceived changes in classroom instruction and behavior management after professional development
- Staff non-administrative cohort 2: Change in raw perceived changes in classroom instruction and behavior management after professional development
- Staff administrative cohort 3: Change in raw perceived changes in classroom instruction and behavior management after professional development

### 9.2 Analysis Population

All participants enrolled to the study who completed the intervention will be included in the analysis population used for primary and exploratory objectives.

The number of participants who either completed the study or discontinued early from the study will be summarized using a CONSORT diagram. Demographic and characteristics at study baseline (1 week prior to intervention) will be summarized.

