### **9.2.1 Per-protocol Population**

For the primary endpoint, participants must have completed the pre and post-CARE assessment to be included in the per-protocol (PP) population.

For the exploratory endpoint, participants must have completed the post-CARE assessment, to be included in the per-protocol (PP) population.

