## **9.3 Analysis Plan**

Summary statistics of the schools and staff in the three cohorts (teacher, staff administrative and staff non-administrative) will be presented using data collected during pre- and post-CARE assessment. We will not share data categorized by role with school districts. We will only share aggregate data grouped by schools with school districts if there are more than 10 participants. If there are fewer than 10 participants at a school, we will group schools together to provide a summary report. If the number of workshop participants for the administrative or non-administrative staff group is less than 10, then these participants will be grouped together and identified as “staff.” Under these circumstances, there will be two cohorts instead of three. Means/medians with standard deviations (and interquartile ranges) will be tabulated.

Descriptive statistics (i.e. number of observations, mean, standard deviation, median and interquartile range) will be presented for continuous variables (e.g. as age, weight, etc.). Other descriptive statistics such as counts, proportions, and/or percentages will be presented to summarize discrete variables (such as race, sex, etc.). All descriptive analyses will be presented by appropriate stratification group and overall as specified under each analysis section.

The analysis and PP populations will be used for the primary and exploratory analyses, unless otherwise specified. A detailed description of statistical methods for all analyses will be prepared and presented in the statistical analysis plan prior to data lock for final analyses.

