### **9.3.1 Primary Analysis**

For the first primary endpoint for the teacher, staff administrative and staff non-administrative cohorts (change in CARE assessment scores after professional development intervention compared to before), the overall proportions will be reported and the change from pre- to post- will be presented in graphical form (bar chart).

95% confidence intervals for raw change in pre-post assessment scores for each assessment will be computed using a non-parametric bootstrap.

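### The primary result is pre-post change among those who finished and responded; the supplied text neither compares them with those lost nor uses the lost participants' baselines in the change estimate

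*Combined protocol and SAP*

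**What the plan says.** The primary objective in section 9.1.1 is to "Examine the impact of a teacher resilience program on mental health and well-being outcomes of K-12 teachers and staff". The endpoint is change in raw score on five instruments, in three cohorts.

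Section 9.2 defines who is analysed: "All participants enrolled to the study who completed the intervention will be included in the analysis population used for primary and exploratory objectives". Section 9.2.1 adds, for the primary endpoint, that "participants must have completed the pre and post-CARE assessment to be included in the per-protocol (PP) population". Section 9.3 says "The analysis and PP populations will be used for the primary and exploratory analyses, unless otherwise specified" and names no third population.

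The primary analysis in section 9.3.1 consists of overall proportions, a bar chart of the change, and this: "95% confidence intervals for raw change in pre-post assessment scores for each assessment will be computed using a non-parametric bootstrap".

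On people who are lost, section 9.2 offers a count: "The number of participants who either completed the study or discontinued early from the study will be summarized using a CONSORT diagram". It also promises a summary of baseline characteristics without naming the population. Section 14.6 uses missing data only as an indirect record of deviations.

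Enrolment under section 4.3 means that "the participant has provided informed consent and completed the pre-intervention CARE assessment battery measures". Section 5.3.1 keeps whatever was collected before a withdrawal. Section 9.3 also says: "A detailed description of statistical methods for all analyses will be prepared and presented in the statistical analysis plan prior to data lock". That later plan is not part of the supplied text.

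**The concern.** Workshop completion is an event after baseline in an optional programme (section 2.1.1) that may take up to four days spread over as many as four months (section 4.2). Partial attendance is therefore possible, and so is silence at one week or two months. If those who leave or fall silent started from different scores, or changed differently, the mean change in the remainder is not the mean change in those who began. The gap can go either way.

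The objective is worded as the programme's impact on teachers and staff, without restriction to finishers who answered. A reader of the results could not tell whether those lost had started out more or less burdened, although the study will hold the data to show it. The bootstrap interval does not help: it measures sampling error in the retained sample, not selection into it.

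**Working it through.** **Reading the text.**
1. Section 9.2 requires completion of the workshop and does not itself require a post score.
2. Sections 9.1.1 and 9.3.1 make the quantity of interest raw pre-post change, which for an individual cannot be formed without a post score. In practice, then, completers who do not respond also drop out.
3. The per-protocol set in section 9.2.1 requires both assessments. Read literally it would admit someone who did not finish but answered; it is still restricted to responders.
4. Everyone enrolled has a baseline battery (section 4.3), apart from items skipped because all questions are optional (section 6.5.1). So baselines exist for those lost.
5. Sections 9.2 to 9.3.1 contain no imputation, weighting, repeated-measures model, lost-versus-retained comparison or sensitivity analysis.

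**Size.** The plan has no figure to reproduce: section 9.4 says no sample size was calculated, and no loss rate, SD or correlation appears anywhere. Every input below is an assumption: unit SDs, a true mean change of -0.20 SD on a symptom scale, pre-post correlation r = 0.6, share lost d = 10-40%, and log-odds of loss b = 0.3-1.0 per SD.

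*Loss depends on baseline only.* Let G be the baseline mean of the lost minus that of the retained. Since (1 - d) × retained mean + d × lost mean = 0, the retained baseline mean is -d × G, and

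completer change - change in all = (1 - r) × d × G.

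Over the assumed range G is about 0.3 to 0.9 SD. Example with 40% lost and b = 1.0 (G = 0.83): 0.4 × 0.40 × 0.83 = 0.133, so completer change is -0.200 + 0.133 = -0.067. Numerical integration with logistic loss gives the following (r = 0.6; each cell lists b = 0.3 / 0.6 / 1.0):

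| Share lost | Higher scorers leave | Lower scorers leave |
|---|---|---|
| 10% | -0.188 / -0.177 / -0.164 | -0.212 / -0.223 / -0.236 |
| 20% | -0.176 / -0.155 / -0.131 | -0.224 / -0.245 / -0.269 |
| 30% | -0.165 / -0.133 / -0.099 | -0.235 / -0.267 / -0.301 |
| 40% | -0.153 / -0.111 / -0.067 | -0.247 / -0.289 / -0.333 |

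At 10-20% lost and b = 0.3 the shift is only 0.012-0.024 SD. In the extreme corner (40% lost, b = 1.0) the two directions give -0.001 and -0.399 at r = 0.4, and -0.134 and -0.266 at r = 0.8. A likelihood-based analysis recovers -0.20 in this setting, but only because the setting makes loss depend on an observed score.

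*Two-month loss depends on the one-week score.* Write r01 for the baseline to one-week correlation in scores and r12 for the correlation of one week with two months, with baseline to two months correlated like r01's value in the change estimate, that is, at the same assumed 0.6 when r01 = 0.6. More generally the bias is (correlation of the one-week score with two months, minus its correlation with baseline) = (r12 - r01), times the shift in the retained one-week mean. At 40% lost and b = 1.0 that shift is 0.332 SD, so the bias is 0.1 × 0.332 = 0.033, 0.2 × 0.332 = 0.066 and 0.4 × 0.332 = 0.133 SD for correlation differences of 0.1, 0.2 and 0.4. It vanishes when the two correlations are equal and changes sign with their difference.

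*Loss depends on the change itself.* Under weak selection the likelihood-based analysis still leaves about (1 - r)(1 + r) / [2(1 - r)] = (1 + r)/2 of the completer bias, which is 80% at r = 0.6. With 40% lost and r = 0.6, simulation puts the remaining share at 0.81 when the correlation between leaving and change is 0.3, and at 0.88 when it is 0.9.

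**The case against.** Several points on the other side are fair.

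- *Some lost participants' baselines may appear in the results.* A reader might infer that the plan ignores them altogether. The documents do not support that: completers who never respond stay in the section 9.2 population, and the descriptive summaries in sections 9.2 and 9.3 could include their baselines. What stands is narrower: nothing planned compares lost with retained or feeds those baselines into the estimate of change.
- *Section 9.3.1 does not say the bootstrap is paired.* A comparison of all available pre and post means is not ruled out. Individual change is the natural reading of raw pre-post change, but it is an inference.
- *Methods are deferred to a later plan.* That plan may add what is missing, so the point concerns the supplied text only. Sections 9.2 to 9.3 nevertheless already fix the populations, and these carry forward unless someone specifies otherwise.
- *Change among completers is a legitimate quantity in a descriptive study.* Agreed, if it is labelled as such.
- *The large figures need extreme inputs together, and modelling cures only some kinds of loss.* Both are true, and the ranges above show it. A reader might also infer that the completer result must flatter the programme. The documents give no basis for a direction.
- *A model for everyone enrolled would be mostly assumption.* This stands. Non-attenders have no workshop date of their own, and follow-up links reach only participating staff through administrators (section 6.5.1), so such a model should be optional.

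**Conclusion.** The point holds as a should-fix, with medium confidence. As written, the primary estimate is change among those who responded and, for the section 9.2 population, also finished. It can differ in either direction from change among those who began, and the supplied text plans nothing that would reveal or adjust for the difference, although the needed baselines are held.

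The effect could be trivial or, in the extreme corner of the assumed inputs, as large as the assumed change; the documents cannot settle which. They do not show that the result will be biased, nor by how much.

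Widening the population would not establish impact either: with a single arm, every version remains uncontrolled pre-post change.

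**What to change.** In sections 9.2 and 9.3.1, or in the statistical analysis plan before data lock:

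1. For each instrument, add a likelihood-based repeated-measures analysis of baseline, one-week and two-month scores, using all available scores from enrolled participants who began the workshop, whether or not they finished.
2. Keep the section 9.2 analysis, labelled 'change among completers who responded'.
3. Tabulate baseline scores of lost versus retained participants.
4. Report one shift analysis: moving the lost participants' mean change by an amount δ moves the overall estimate by share lost × δ, for example 0.30 × 0.3 SD = 0.09 SD.
5. State that the model removes bias only from loss related to observed scores, and describe all results as uncontrolled pre-post change.

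An analysis of all enrolled is optional.

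The cost is wording, modest programming and reliance on missing at random. Person-level linking of pre and post scores is already needed for raw change. A record of who began the workshop is also required. Section 9.2 already implies one of who completed it, but the documents describe no attendance source (section 11 has all data entered by participants), so this may be new data capture. If the model is declined, the label and the baseline table are inexpensive and would still answer the core of the point.
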